# 6. Power Calculations

Minimum detectable rate ratios for colon, breast, prostate and any cancer (except non-melanoma skin cancer) are presented below. The MedAssurant database contains approximately 47,227 new glargine users and 9899 new NPH users. Median follow-up time is approximately 2 years in each of the treatment groups. Age and sex-specific SEER cancer incidence rates were used to compute age and sex-adjusted cancer incidence rates that were standardized to the MedAssurant population. Additional adjustments were made to take into account cancer incidence rates in the diabetic population (Renehan, et al, The Lancet, June 2010). Using these cancer incidence rates, the following risk ratios are able to be detected with approximately 80% power at the  $\alpha$  = 0.05 level (two-sided test).

	Minimum RR (MedAssurant only)
Any cancer	1.2
Colon only	1.72
Breast (females)	1.53
Prostate (males)	1.58

When the MedAssurant data is pooled with the Solucia data, the power will increase. Ideally, this study would have power to detect a clinically meaningful hazard ratio of glargine versus NPH. Based on the June 2009 Diabetologia reports which examined the relationship between glargine and cancer, hazard ratios implicating glargine insulin as associated with cancer were generally greater than 1.5. The new user analysis has sufficient power to detect a hazard ratio less than 1.58 for three of the four endpoints.

# 7. Projected Timeline

Draft analysis results available	March 2012
Final analysis results available	June 2012
Manuscript submitted	Sept 2012

#### Appendix A New User Algorithm

#### **Definitions/Conventions**

Washout Period (WP) = minimum length of time that a patient must be drug-free prior to becoming eligible for the new user cohort Grace Period (GP) = maximum length of time that a user can go without a drug before being considered discontinued from drug use

 $W_i$  = Days since start of washout period prior to 1st RX fill of ith period of use for the patient  $G_i$  = Days from last day covered by the jth RX fill to the (j+1)th RX fill date

#### **Cohort Eligibility**

[figure not shown]
If  $W_1 > WP$  then patient's period of drug use is eligible for the new user cohort.

If  $W_i$  > WP and i>1 then patient's period of drug use is eligible for new user cohort **IFF** the analysis allows for previous users to become new users.

If i=1 then patient's period of drug use is eligible for the prevalent user cohort regardless of the value of  $W_1$ 

# **Drug Discontinuation/Censor Date**

If  $G_j > GP$  then the patient is considered discontinued from drug use on the last day covered by the jth RX fill + GP If (End of Enrollment) – GP < (Last Day Covered by an RX Fill) then the patient is censored at End of Enrollment

#### **Algorithm**

- 1. Set (Start of Washout Period) = (Start of Continuous Enrollment).
- 2. Set (Index Date) = (1st RX Fill Date following Start of Washout Period). Let *W* = (Index Date) (Start of Washout Period). Flag the period of drug use for cohort eligibility based on the following criteria:
  - a. If this is the patient's first RX of record, then flag as the index date for the prevalent user cohort.
  - b. If this is the patient's first RX of record and W > (Washout Period), then flag as the index date for the primary new user cohort.
  - c. If W > (Washout Period), then flag as the index date for the secondary new user cohort.
- 3. Set (Last Day Covered) = (Index Date) + (Days Supply).
- 4. Let G = (RX Fill Date) (Previous Last Day Covered). Sequentially cycle through the subsequent prescription claims for the patient, applying the appropriate step below, until (Discontinuation Date) is set:
  - a. If G > (Grace Period) then set (Discontinuation Date) = max(Previous Last Day Covered, Date of RX Fill) + (Days Supply) + (Grace Period).
  - b. If G <= (Grace Period), set (Last Day Covered) = max(Previous Last Day Covered, Date of RX Fill) + (Days Supply). If (Last Day Covered) + (Grace Period) > (End of Continuous Enrollment) and the patient has no additional RX claims with (RX Fill Date) <= (End of Continuous Enrollment), then set (Discontinuation Date) = (End of Continuous Enrollment). Otherwise, repeat Step 3 for the next prescription.

- 5. Output a record containing Index Date, Discontinuation Date, and the cohort inclusion flags set in Step 2.
- 6. Set (Start of Washout Period) for the next period of use:
  - a. If the patient is continuously enrolled from (Discontinuation Date) to the next (RX Fill Date), set (Start of Washout Period) = (Discontinuation Date) + 1.
  - b. If the patient has a gap in enrollment between (Discontinuation Date) and the next (RX Fill Date), set (Start of Washout Period) = (Start of Next Period of Continuous Enrollment).
- 7. Repeat Steps 2-7 for the patient's remaining RX fills.

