Stopping, switching, augmenting: Because we are interested in potential harm, the primary analysis will be as treated. Therefore, in the primary analysis that compares new users of glargine with new users of NPH, patients stopping the corresponding drug (glargine or NPH), switching to another long-acting insulin (including detemir), or augmenting with another long-acting insulin will be censored at that point in time. Patients who take a premixed analog insulin during follow-up will be treated in a similar manner (i.e. censored at that point in time). Patients who do not refill their insulin prescription within a period equal to the total days of supply (plus a 6 months grace period) will be treated as if they stopped taking insulin at the end of that period (i.e. they will be censored at the last prescription date plus [the days of supply plus 6 months]). If no information on days of supply is available, an informed guess will be made based on the specific study site (i.e., median days of supply).

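### Appendix A Step 4 dates discontinuation from the fill after a long gap and gives permanent stoppers no date, contradicting Section 5.5 and Appendix A's own censor-date rule

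*Protocol*

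**What the plan says.** Three places in the protocol define when a patient stops.

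- **Section 5.5, paragraph on stopping, switching and augmenting.** "Because we are interested in potential harm, the primary analysis will be as treated". Patients who do not refill within the days of supply plus 6 months are treated as having stopped: "they will be censored at the last prescription date plus [the days of supply plus 6 months"].
- **Appendix A, Drug Discontinuation/Censor Date.** When the gap after fill j exceeds the grace period (GP), "then the patient is considered discontinued from drug use on the last day covered by the j th RX fill + GP". The definitions at the start of the appendix measure that gap from the last day covered by fill j to fill j+1, so fill j is the one before the gap.
- **Appendix A, Algorithm, Step 4.** G is the current fill date minus the previous last day covered. If G exceeds the grace period, Step 4a says "then set (Discontinuation Date) = max(Previous Last Day Covered, Date of RX Fill) + (Days Supply) + (Grace Period"). If it does not, Step 4b moves the last day covered forward and closes the episode at the end of enrolment under one condition: "If (Last Day Covered) + (Grace Period) > (End of Continuous Enrollment) and the patient has no additional RX claims" up to that end. In every other case: "Otherwise, repeat Step 3 for the next prescription".

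Step 2b flags the primary new user cohort, and Step 5 writes out the discontinuation date.

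**The concern.** Section 5.5 and the censor-date rule agree with each other; Step 4 does not agree with them. There are three faults.

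1. Step 4a is reached only when the current fill lies more than a grace period after the previous last day covered. The maximum in its formula is therefore always the post-gap fill. The episode runs across the gap, through the resumed supply, and through a second grace period.
2. A patient who never refills does not reach Step 4a, because there is no later fill. Step 4b closes the episode only if the grace period would outlast enrolment. Otherwise it points to a next prescription that does not exist, and no date is set.
3. Step 3 sets the last day covered to the index date plus days' supply. Repeating it at each fill would discard the coverage built up in Step 4b.

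The stopping date ends primary follow-up and starts the 3- to 24-month lag analyses in Section 5.6.2. In the as-treated design it also determines who contributes to the later follow-up strata, which Section 5.6.1 treats as an indicator of cumulative dose. UNC-CH and MedAssurant analyse their data separately, and site differences in hazard ratios are to be examined, so both groups need one unambiguous rule.

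**Working it through.** **Inputs.** The grace period is 6 months (Sections 5.1 and 5.5), taken here as GP = 183 days. Days' supply is D = 30, matching the one-month supply in Section 5.1; D = 90 is an assumed alternative. The one stated figure that uses the grace period is the look-back, and it reproduces: 1 + 6 + 12 = 19 months. No power or sample-size figure is involved.

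**Patient who restarts after a long gap.** Let L be the last day covered before the gap and G the gap.

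- Section 5.5 and censor-date rule: stop = L + GP.
- Step 4a: the post-gap fill is on day L + G, so stop = L + G + D + GP.
- Difference = G + D. This splits into G − GP (uncovered days beyond the grace period), D (resumed supply) and GP (a second grace period).

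Take fills on days 0, 30 and 60 with D = 30, so L = 90. This history satisfies the second-prescription rule for MedAssurant. The Section 5.5 date is 90 + 183 = day 273.

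| Gap G | Refill day | Step 4a date | Excess (G + D) | Uncovered beyond grace (G − GP) |
|---|---|---|---|---|
| 184 | 274 | 487 | 214 | 1 |
| 270 | 360 | 573 | 300 | 87 |
| 300 | 390 | 603 | 330 | 117 |
| 365 | 455 | 668 | 395 | 182 |
| 600 | 690 | 903 | 630 | 417 |

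For G = 300 the 330 days are 117 + 30 + 183. With D = 90 and fills on days 0, 90 and 180, L = 270. A gap of 365 days then gives 453 under Section 5.5 and 635 + 90 + 183 = 908 under Step 4a, an excess of 455.

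**Patient who never refills.** Same fills, last on day 60, so L + GP = 273.

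- Enrolment ends day 200: 273 > 200, so Step 4b gives day 200. The rules agree.
- Enrolment ends day 273, 730 or 1095: the condition 273 > end of enrolment fails and no further fill exists. Step 4 gives no date; Section 5.5 gives day 273.
- If a programmer filled the missing date with end of enrolment (an assumption; the protocol does not say so), the excess would be 730 − 273 = 457 days or 1095 − 273 = 822 days.

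**Repeating Step 3 literally.** For monthly fills on days 0 to 690, the last day covered returns to day 30 each time. At the day-240 fill, G = 240 − 30 = 210 > 183, so Step 4a stops the patient at 240 + 30 + 183 = day 453. The Section 5.5 date is 720 + 183 = day 903. This error shortens follow-up.

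**Re-initiation.** The post-gap fill on day L + G always precedes the Step 4a date, and Step 6 starts the next washout after that date. The post-gap fill can therefore never be an index fill. With G = 600, the Section 5.5 date gives a washout from day 274 to day 690, which is 416 days and exceeds 12 months (365 days). That fill would qualify as a further instance of new use, but Step 4a absorbs it into the first episode.

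**The case against.** The strongest reply is that the intended rule is not in doubt. Section 5.5 states it in the main text, Appendix A repeats it just above the algorithm, and Section 5.5 covers the patient who never refills without needing a later fill. A careful programmer would follow those. This stands as a limit: the harm is conditional on Step 4 being coded as written. It does not remove the fault, because Step 4 is the operational text and its formula cannot be read into agreement. If the fill date in Step 4a were taken as the pre-gap fill, the maximum would be the previous last day covered and the result would still be one days' supply too late.

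Stronger readings that the protocol does not support:

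- **That off-drug time is counted as exposed in the primary analysis.** For permanent stoppers the date is undefined, which is not the same as exposed to the end of enrolment. For restarters, part of the excess is resumed supply, and the first grace period counts as exposed under either rule.
- **That G + D days is a guaranteed minimum excess.** Cancer, death, a membership gap, end of study, switching, augmenting or use of a premixed analog can end follow-up sooner.
- **That all on-treatment time comes from this algorithm.** Section 5.2 says the Ochsner and Partners records do not hold every later prescription, and in MedAssurant follow-up starts at the second prescription.
- **That the hazard ratio is pulled toward 1.** Step 4a lengthens exposed time, but literal repetition of Step 3 shortens it. Dilution would also require that risk does not persist after stopping, which the planned lag and ITT analyses leave open.
- **That lost re-initiations affect the primary result.** Section 5.1 uses only the first instance. The loss affects the promised count of later instances and a sensitivity analysis planned if resources allow.

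**Conclusion.** The point holds as an internal contradiction in the algorithm that outputs the discontinuation date for the primary new user cohort. Step 4a is later than the rule in Section 5.5 and the censor-date paragraph by exactly G + D: 330 days for a 300-day gap and a 30-day supply, before any other censoring event, against a median follow-up of about 2 years in Section 6. Step 4 assigns no date to a patient who never refills and remains enrolled through the end of the grace period, and its loop instruction points to the wrong step.

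If Step 4a is coded as written, primary as-treated follow-up for restarters includes uncovered time beyond the grace period and a second grace period, and the post-gap fill cannot open a new episode. The day counts assume GP = 183 days and the stated supplies; the difference G + D does not depend on GP. The protocol gives no frequency of long gaps or of stopping, so neither the share of person-time affected nor the size or direction of any effect on the hazard ratio can be computed. It should be corrected before exposure time is programmed.

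**What to change.** Bring Step 4 into line with Section 5.5 and the censor-date rule:

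1. **Step 4a:** if G exceeds the grace period, set the discontinuation date to the previous last day covered plus the grace period.
2. **New branch:** if there is no further fill and the last day covered plus the grace period is on or before the end of continuous enrolment, set the discontinuation date to the last day covered plus the grace period.
3. **Step 4b:** return to Step 4, not Step 3, for the next prescription.
4. **Post-gap fill:** leave it to the existing Steps 5 to 7. It should not go straight to Step 2, because that would skip the washout reset in Step 6.
5. **Check:** have both analysis groups run the rule on a few worked fill histories: a restart after a long gap, a permanent stopper enrolled past the grace period, a stopper who leaves enrolment earlier, and a continuous monthly refiller.

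The cost is a wording change and a few lines of code. On-treatment follow-up will be somewhat shorter than under Step 4a read literally.

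### Appendix A Step 4b loops back to Step 3, which resets coverage to the index fill; with that pointer corrected, 4b still carries unused supply forward where Section 5.5 does not

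*Protocol*

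**What the plan says.** Appendix A prints the algorithm that turns prescription fills into a period of use.

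- **Step 2** fixes the index date as the first "RX Fill Date following Start of Washout Period".
- **Step 3** reads "Set (Last Day Covered) = (Index Date) + (Days Supply").
- **Step 4** says "Sequentially cycle through the subsequent prescription claims for the patient, applying the appropriate step below", and computes the gap G from the previous last day covered.
- **Step 4b**, for a refill within the grace period, says "set (Last Day Covered) = max(Previous Last Day Covered, Date of RX Fill) + (Days Supply"). Unless its end-of-enrolment condition is met, it then says "Otherwise, repeat Step 3 for the next prescription".

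The prose of the same appendix defines the gap as "Days from last day covered by the j th RX fill to the (j+1) th RX fill date" (Definitions/Conventions). When the gap exceeds the grace period, "then the patient is considered discontinued from drug use on the last day covered by the" jth fill, plus the grace period (Drug Discontinuation/Censor Date).

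Section 5.5 states the stopping rule for the primary as-treated analysis: patients who do not refill in time are treated as having stopped, and "they will be censored at the last prescription date plus [the days of supply plus 6 months"].

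**The concern.** The index date does not move during a period of use. Returning to Step 3 after each refill therefore replaces the coverage just computed with the coverage of the first fill. Every later gap is then measured from that first fill, and it grows until a patient who has never stopped exceeds the grace period.

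If the loop is read as returning to Step 4, that problem goes away and a different one appears. The max() in 4b adds each new supply to whatever is left over, while the Section 5.5 formula counts supply from the last prescription date only.

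The date at stake sets person-time and events in the primary as-treated analysis of the claims data, and the lagged-censoring analyses in Section 5.6.2 start from it. Section 5 has UNC-CH analyse Solucia and MedAssurant analyse its own database. The site hazard ratios are then pooled and compared for heterogeneity, so both groups need the same rule.

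**Working it through.** The protocol gives no figure of its own here, so the check is to run the printed steps on simple fill histories.

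**Inputs.** Grace period 6 months, taken as 183 days. Supply of 30 days, from the one-month estimate in Sections 5.1 and 5.2; a 90-day supply is an assumption. Illustrative enrolment of 730 days, from the median follow-up of about 2 years in Section 6. The index fill is day 0.

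**1. Loop as printed, refills exactly on time.** Last Day Covered returns to day 0 + supply before each test, so G = fill day − supply.

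- 30-day supply: G exceeds 183 at the first fill after day 213 (30 + 183), which is day 240, where G = 240 − 30 = 210. Step 4a then gives 240 + 30 + 183 = day 453. The Drug Discontinuation/Censor Date rule, applied to the same reset coverage, gives 30 + 183 = day 213.
- 90-day supply: the first fill after day 273 (90 + 183) is day 360, where G = 360 − 90 = 270. Step 4a gives 360 + 90 + 183 = day 633.
- Taking the grace period as 180 to 184 days moves the 30-day date under 4a only between days 450 and 454.

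With 730 days enrolled, the 4a dates would lose 730 − 453 = 277 days (38%) for the 30-day filler and 730 − 633 = 97 days (13%) for the 90-day filler. A 30-day filler enrolled for no more than 240 days is unaffected.

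**2. Loop returned to Step 4.** For on-time refills, each fill falls on the previous last day covered, so G = 0 throughout. In every gap-free history run (30-, 60- and 90-day supplies, and a 30-day supply refilled every 25 days; enrolment of 1 to 4 years), the date is the end of continuous enrolment, with or without carry-over.

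**3. Carry-over, with the loop returned to Step 4.** A 30-day supply is refilled every 25 days for 2 years (fills on days 0 to 725, 30 fills), and the patient then stops.

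- 4b coverage ends on day 30 × 30 = 900. Adding grace gives day 1083.
- Section 5.5 coverage ends on day 725 + 30 = 755. Adding grace gives day 938.
- The difference is 145 days. It is zero if enrolment ends by day 938 and reaches 145 only if enrolment runs to day 1083.

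Milder early refilling gives less. Every 28 days: 27 × 30 = 810 against 728 + 30 = 758, or 52 days. A 90-day supply every 80 days: 10 × 90 = 900 against 720 + 90 = 810, or 90 days. The same enrolment condition applies.

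**4. Where carry-over acts.** It affects the gap test and the date under the Drug Discontinuation/Censor Date rule. It cannot affect the date set by 4a: when G exceeds the grace period, the new fill is later than the previous coverage end, so max() returns the fill date. A patient who stops for good while still enrolled reaches neither 4a, which needs a later fill, nor the end-of-enrolment branch of 4b. That patient's date has to come from the prose rules.

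**The case against.** The appendix makes its intent clear. Step 4's opening sentence, the definition of the gap, the Drug Discontinuation/Censor Date rule and the term for previous coverage inside Step 4 all require coverage to move forward fill by fill. Against these stands one step number that is off by one, and a programmer who reads the whole page would repair it. This stands, and it limits the first half of the point to what happens if the text is coded as printed.

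Days 453 and 633 also depend on 4a dating discontinuation from the fill after the gap, which itself disagrees with the prose rule. This stands too, and is why day 213 is given beside day 453.

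The two halves cannot occur together: if Step 3 really is repeated, it overwrites the carried-forward supply. Correct; the second half applies only after the pointer is repaired.

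A reader might infer that carry-over counts months off the drug as exposed. The documents do not show that: the carried supply was dispensed, and whether to count it is a convention. Section 5.5's mention of a total supply leaves some room, although its bracketed formula does not. The planned lags of 3 to 24 months and the ITT analysis also cover shifts of this size.

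A reader might also infer that the two groups will code the steps differently and create spurious heterogeneity. Nothing in the protocol says so, and Section 3 gives UNC-CH the coordinating role. What remains is that two coverage rules are printed and neither is given precedence.

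**Conclusion.** Step 4b is wrong as printed. Followed literally, it flags uninterrupted users as discontinued: at day 240 with 30-day fills (dated day 453 under 4a, or day 213 under the prose rule) and at day 360 with 90-day fills (dated day 633 under 4a). These figures assume a 183-day grace period and regular fills. The pointer is most likely a slip for Step 4, and returning the loop there removes every false discontinuation in the histories tested.

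It is tempting to conclude that the 24+ month follow-up stratum would be empty. The documents do not support that as a general statement. It requires the slip to be coded as printed, against the rest of the appendix, and it extends results for idealised regular refillers to a whole cohort whose fill patterns are not given.

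The mismatch between 4b and Section 5.5 on unused supply is real but smaller. It concerns early refillers who stop while still enrolled, by up to 145 days in the 25-day example. The protocol gives no basis for estimating how many patients are affected by either problem. This is an operational rule to correct before coding, not a flaw in the design.

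**What to change.** 1. At the end of Step 4b, change the step to be repeated from Step 3 to Step 4, so that Step 3 runs once per period of use.
2. Reconcile the coverage and discontinuation-date rule across Steps 4a and 4b, the Drug Discontinuation/Censor Date text and Section 5.5, and state one rule in all of them. It should say whether unused supply is carried forward, from which fill the date is counted, and what date applies to a patient who stops for good while still enrolled. The choice belongs to the study team.
3. Before analysis, have UNC-CH and MedAssurant run the corrected steps on the same small set of test fill histories: on-time refills, early refills, a gap followed by a refill, and a final stop during enrolment. Confirm that the dates agree.

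The pointer is a one-word correction. The reconciliation takes somewhat more drafting because four pieces of text must agree, and the test histories need a short code check. No new data are needed, and there is no cost to patients.
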